6.2 AEs and SAEs

6.2.1 Adverse events (AEs)

Adverse events are defined as any undesirable experience occurring to a patient during the study, whether or not considered related to the trial procedure or the experimental intervention. All adverse events reported spontaneously by the patient or observed by the general practitioner, his staff, or the investigator will be recorded.

6.2.2 Serious adverse events (SAEs)

During the control period, patients receive care as usual, so no AE and SAE are expected, and if they do, they are part of the usual care process and cannot be considered a consequence of participating in the study.

We will instruct all general practitioners to warn the investigator about every SAE occurring during the study, i.e. psychosis, (attempted) suicide, requirement of the crisis intervention team, and death. We will examine every case to see whether the trial procedure or the intervention caused the SAE. The investigator will report all SAEs to the sponsor without undue delay after obtaining knowledge of the events.

The sponsor will report the SAEs through the web portal *ToetsingOnline* to the accredited METC that approved the protocol, within 7 days of first knowledge for SAEs that result in death or are life threatening, followed by a period of maximum 8 days to complete the initial preliminary report. All other SAEs will be reported within a period of maximum 15 days after the sponsor has first knowledge of the serious adverse events.

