5.1.2 Secondary study parameters

- Health-related quality of life will be measured with the EuroQol-5D-5L (EQ-5D). This instrument is available in a validated Dutch translation. The EQ-5D comprises five domains: mobility, self-care, usual activities, pain/discomfort, and anxiety/depression. The EQ-5D index is obtained by applying predetermined weights to the five domains, and ranges from 0 to 1, where a score of 1 equals perfect health.
- We will measure change in side effects using the Liverpool University Neuroleptic Side Effect Rating Scale (LUNSERS) (17).
- We will use the 8-item Client Satisfaction Questionnaire (CSQ-8) to measure participants' satisfaction with care. This questionnaire is recommended for use in psychiatric patients (20),(21) and has a Dutch validated version (22).
- Number of groups meetings (Step 1), multidisciplinary meetings (Step 2), and GP contacts (Step 3);
- Number and content of individualized treatment plans;
- Percentage of patients who attend group meeting (Step 1);
- Percentage of patients who attend multidisciplinary meeting (Step 2);
- Percentage of patients who contact GP to discuss individualized treatment plan (Step 3);

- Reasons for drop-out.
- Numbers and type of (serious) adverse events.
- Numbers and type of advice given in Step 3 of the intervention, and numbers and type of advice followed up or executed.
- Healthcare utilization as measured with the Dutch version of the Treatment Inventory of Costs in Patients with psychiatric disorders (TIC-P) questionnaire;
- Costs related to health care, such as medication, visits to the general practice, visits to relevant medical specialists.
- Patient costs, such as travel costs, time costs and over the counter medication
- Costs in other sectors, such as health promotion costs within budget of municipalities

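### Section 6.2.2 rules in advance that control-period adverse events are not expected and not study-related, contradicting the recording and causality rules around it and inviting unequal reporting between conditions

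*Protocol*

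**What the plan says.** The first paragraph of Protocol 6.2.2 concerns the control period. Because patients then receive usual care, it continues "so no AE and SAE are expected, and if they do, they are part of the usual care process and cannot be considered" a result of study participation.

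The surrounding text sets different rules:

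- Section 6.2.1 defines an AE as "any undesirable experience occurring to a patient during the study, whether or not considered related to the trial procedure or the experimental intervention" and adds: "All adverse events reported spontaneously by the patient or observed by the general practitioner, his staff, or the investigator will be recorded".
- The second paragraph of 6.2.2 says: "We will instruct all general practitioners to warn the investigator about every SAE occurring during the study". It lists these SAEs as "psychosis, (attempted) suicide, requirement of the crisis intervention team, and death" and then promises: "We will examine every case to see whether the trial procedure or the intervention caused the SAE".
- Section 5.1.2 makes the result a secondary parameter: "Numbers and type of (serious) adverse events".

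Four other statements bear on the point. Section 4 makes usual care before TACTIC the comparator. Section 5.2 says clusters cannot be blinded. The Summary and section 8.4 name mental destabilisation after a medication change as the potential risk of participation and expect it to be low. Section 6.4 installs no DSMB, on the ground that the study is low-risk.

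**The concern.** The opening paragraph makes two statements that should not be fixed in advance: that nothing will happen under control, and that whatever does happen is unrelated to the study. The first is a poor premise for this population. The second settles causality before any case has been seen.

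What is at stake is the comparison of safety between conditions. The people who report events know which condition the patient is in. AEs are captured only if volunteered or noticed, and TACTIC adds a multidisciplinary meeting and an action-plan consultation at which they can be noticed. A practice that takes the opening paragraph at face value has a reason to report less before TACTIC than after it. Under-reporting in control would make background events look like harm from TACTIC. Conversely, a real excess could be discounted because the control figure is not trusted. The listed SAEs largely describe the very risk that the protocol names, and no independent board would notice a reporting imbalance.

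**Working it through.** The protocol gives no (S)AE rate, margin or power, so there is no stated figure to reproduce. The check has three parts.

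**1. The statements side by side**

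| Question | 6.2.2, first paragraph | 6.2.1 and 6.2.2, second paragraph |
|---|---|---|
| Are control-period events anticipated? | No | Collection covers the whole study, with no exemption for control |
| Does relatedness decide what counts? | Control events are assigned to usual care | An AE counts "whether or not considered related to the trial procedure or the experimental intervention" |
| Who decides causality of an SAE? | Decided in advance: not due to participation | Examined case by case |

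The last row is a direct contradiction. The case review covers the trial procedure as well as the intervention, and some trial procedures, such as the baseline questionnaires (section 5.3), come before TACTIC. Under the first paragraph the number of study-related control events is zero by rule. Under the second paragraph it is a finding.

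**2. Is it plausible that no control SAE occurs?**

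Inputs from section 3.4: 480 patients. With four steps of equal size (assumed), 120 patients per step. Two assumptions are needed because the protocol does not supply them:

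- *Control time.* Figure 1 is not shown. Layout A assumes 20 months of follow-up for everyone, with 0, 5, 10 and 15 months under control by step: 120 × (0 + 5 + 10 + 15) / 12 = 300 control patient-years, and 120 × (20 + 15 + 10 + 5) / 12 = 500 after TACTIC. Layout B reads Table 1 literally, with about one month between screening and the meeting: 480 × 1/12 = 40 control patient-years.
- *Background SAE rate.* Assumed 0.01 to 0.10 per patient-year.

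Expected control SAEs = rate × control time. Poisson probability of none = exp(−expected).

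| Rate per patient-year | A: expected | A: P(none) | B: expected | B: P(none) |
|---|---|---|---|---|
| 0.01 | 3 | 0.050 | 0.4 | 0.67 |
| 0.02 | 6 | 0.0025 | 0.8 | 0.45 |
| 0.05 | 15 | < 0.001 | 2 | 0.14 |
| 0.10 | 30 | < 0.001 | 4 | 0.018 |

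Under layout A, a control period without an SAE would be unusual at every rate shown. Under layout B it could well happen at the low rates, but only because control time is short and not because usual care is free of such events. The statement also covers AEs of any kind, for which zero is less plausible still.

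**3. What unequal reporting would do**

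Let *c* be the share of control events reported, with complete reporting after TACTIC. Then

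apparent rate ratio = true rate ratio / *c*.

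With a true ratio of 1: 1/0.90 = 1.11, 1/0.75 = 1.33, 1/0.50 = 2.0. Background rate and patient-time cancel, so these values do not depend on the layout. They do depend entirely on *c*, which nothing in the protocol lets one estimate. If 6.2.1 and the second paragraph of 6.2.2 were followed in full, *c* = 1 and there is no distortion.

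**The case against.** A reader might infer that the trial has no valid control rate for adverse events. The protocol does not support that. The opening paragraph speaks of expectation and attribution, not of collection. Section 6.2.1 and the second paragraph of 6.2.2 cover the whole study, and section 6.3 requires SAE reporting to its end. None exempts the control period. If these rules are followed, control events are counted.

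Other points on that side also carry weight:

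- Under-reporting is a risk, not a stated rule. The instruction that the protocol says practitioners will receive is to report every SAE. The listed SAEs are major events that are unlikely to surface only because TACTIC adds contacts, so that argument applies mainly to minor AEs.
- Mental state and side effects are also measured systematically. The MHI-5 is a primary outcome and the LUNSERS a secondary one, and both are completed at baseline and at the 5-monthly follow-ups. Evidence on destabilisation does not rest on spontaneous reports alone.
- Listing numbers of events in 5.1.2 does not exclude rates. Tabulation by condition with patient-time can be left to a SAP.
- No primary inference depends on (S)AEs.

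These points limit the concern but do not remove it. The contradiction on causality lies within a single section, and no analysis plan can recover events that were never reported.

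**Conclusion.** The concern stands as a wrong and self-contradictory rule on expectation and causality in the control period. It creates a risk of differential ascertainment and attribution in an unblinded trial with passive AE capture and no DSMB, on the one risk that the protocol names for the intervention.

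The size of any bias is unknown. The ratios of 1.11 to 2.0 are illustrations that follow from assumed control completeness of 90% to 50%, and are not estimates. The implausibility of an event-free control period rests on an assumed SAE rate and on a layout that cannot be confirmed without Figure 1. The contradiction itself rests on the text alone. Because (S)AEs are a secondary parameter with no stated test, this is a matter of moderate weight that should be corrected. It does not threaten the primary analysis.

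**What to change.** - Delete the first paragraph of 6.2.2, or reconcile it with 6.2.1 and with the paragraph that follows it.
- State that AEs and SAEs are recorded, reported and assessed for causality by the same rules in both conditions, from informed consent to the last visit.
- Add one item to the existing 5-monthly visit form asking whether any of the listed events has occurred since the previous visit, so that capture does not depend on spontaneous reports alone.

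The cost is a few sentences of protocol text, one form item and a few more control-period reports. No extra visit is needed. Tabulating events by condition with patient-time is advisable, but may be left to the SAP.

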Although these factors may contribute as independent risk factors for cardiometabolic dysfunction and cardiovascular disease, having a severe mental illness itself is also an important independent risk factor (5), as well as antipsychotic treatment, particularly for certain drugs and for vulnerable patients (9). In a large prospective open cohort study in England, severe mental illness was associated with a 14% increased risk for women and a 13% increased risk for men (11). This was independent of the risk associated with atypical antipsychotics. Atypical antipsychotics were associated with an increased cardiovascular risk of 29% in women and 15% in men. In addition, antipsychotics cause a dose-related increased risk of sudden cardiac death (12). All in all, this results in a 8-20 years reduction in life expectancy (11).

In the Netherlands, it is common that psychiatrists initiate treatment with antipsychotic medication, but when patients reach a stable state, care is shifted to the general practice. This includes monitoring of treatment effects, adherence and side effects, as well as management of cardiovascular risk. However, monitoring of usage and effects of antipsychotic treatment as well as cardiovascular risk screening in patients with severe mental illness or on antipsychotic treatment is currently not sufficient (5-7). Lifestyle factors

are relatively easy to measure, but are barely considered for screening. Baseline testing of important physical parameters, prior to starting antipsychotic medication, is insufficiently performed (5). This is a serious aspect that needs to be addressed, even more since the adverse effects of antipsychotic medication may also impair the patient's adherence to treatment (13).

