on antipsychotic use, and the QRISK3 score at baseline (see Methods 6.1.2. Secondary study parameters).

During the multidisciplinary meeting, the participating patient (and carer), the general practitioner, a psychiatrist, the primary care nurse, and if desired an experience expert (patient coach who lived the experience) will review the patient's antipsychotic use and all other relevant medication (if applicable). Also, possible cardiovascular risk factors will be addressed, such as smoking status, blood pressure, Body Mass Index, blood glucose and cholesterol levels. The multidisciplinary meeting will result in a set of individualised treatment suggestions, including advice on antipsychotic use (e.g. continuation, deprescribing, or switching) and reducing cardiovascular risk.

Step 3: A week after the multidisciplinary meeting, the patient has a consultation with the general practitioner during which the set of individualised treatment suggestions will be translated into an action plan through shared-decision making. This shared-decision making process will benefit the adherence and outcome of the plan. The plan will also define the tasks and responsibilities of the various healthcare providers. Potential actions are altering antipsychotic use, initiating antihypertensive medication or statins, referral to the chronic care nurse (in Dutch: POH-S) for example for smoking cessation, referral to the primary care mental health nurse (in Dutch: POH-GGZ), the dietician, the physical therapist, or a life style coach.

The effects of TACTIC in addition to usual care will be compared to usual care alone, in which patients will be their own comparator, prior to treatment initiation.

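### Section 6.2.2 limits GP notification of SAEs to four events, so non-fatal infarction, stroke and serious somatic admissions are at most recorded as AEs and fall outside expedited reporting

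*Protocol*

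**What the plan says.** **SAE notification (Protocol 6.2.2).** GPs are to be instructed to warn the investigator about "every SAE occurring during the study, i.e. psychosis, (attempted) suicide, requirement of the crisis intervention team, and death". The investigator then examines each case for a causal link to the trial procedure or the intervention, and passes all SAEs to the sponsor without undue delay. The sponsor reports to the METC "within 7 days of first knowledge for SAEs that result in death or are life threatening". For the rest, "All other SAEs will be reported within a period of maximum 15 days".

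**AE recording (6.2.1, 6.3, 5.1.2).** The AE definition is wide: "Adverse events are defined as any undesirable experience occurring to a patient during the study", related or not. The recording rule is "All adverse events reported spontaneously by the patient or observed by the general practitioner, his staff, or the investigator will be recorded". Section 6.3 follows AEs until they resolve or stabilise. Section 5.1.2 lists the number and type of both AEs and SAEs as a secondary parameter.

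**Context.** Section 3.2 requires a 10-year cardiovascular risk of at least 5%, and section 3.3 excludes established cardiovascular disease. Under Step 3 in section 4, "Potential actions are altering antipsychotic use, initiating antihypertensive medication or statins". Section 6.4 states that there is no DSMB and no interim analysis.

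**The concern.** The four items cover mental destabilisation and death. Serious non-fatal somatic events are absent. That fits poorly with a trial that recruits on cardiovascular risk, aims to lower it, and may lead to new antihypertensives or statins or to a change of antipsychotic. Because established cardiovascular disease is an exclusion, a non-fatal infarction or stroke during follow-up would usually be a first event of the kind the trial hopes to prevent.

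At stake is the speed and completeness of safety oversight while the trial runs. GPs start the reporting chain. If their instruction omits a class of events, the later steps in 6.2.2 do not begin for that class. The split between AEs and SAEs in the final report would also be wrong for somatic events. The SAE definition belongs in the protocol, so this is not a matter left to an analysis plan.

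**Working it through.** The protocol states no figure for this point, so the check is mainly a comparison of text, followed by a rough estimate of how many events could be affected.

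**Step 1: is the list closed?** The linking term in 6.2.2 means *that is*, so read literally the four items are the definition given to GPs. The other safety text (Summary, 6.1, 6.2.1, 6.3, 8.4) contains no general seriousness criterion such as hospital admission or lasting disability. The phrase about life-threatening SAEs in 6.2.2 sorts SAEs by reporting time and does not add events to the list.

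**Step 2: follow two events through the rules as written.**

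| Stage | Attempted suicide | Non-fatal stroke with admission |
|---|---|---|
| On the 6.2.2 list | yes | no |
| Recorded as an AE if reported or observed (6.2.1) | yes | yes |
| Followed until resolved or stable (6.3) | yes | yes |
| GP warns investigator (6.2.2) | required | not required |
| Case-by-case causality review (6.2.2) | required | not required |
| To sponsor without delay, to METC in 7 or 15 days (6.2.2) | required | not required |
| Counted under 5.1.2 | as SAE | as AE only |

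The second column applies equally to a non-fatal infarction or to an admission for collapse after a newly started drug. Capture under 6.2.1 is also passive: it depends on spontaneous report or observation, and no time limit is given for passing the record on.

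**Step 3: reporting classes against the list.** The 7-day class covers fatal and life-threatening SAEs. On the list, death fits, and a suicide attempt can fit. Psychosis and crisis-team involvement fall in the 15-day class. Both classes therefore have members. The life-threatening class is nearly empty, though, which suggests that a wider notion of seriousness may have been intended.

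**Step 4: how many cardiovascular events might arise?**

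Inputs from the protocol: 32 clusters with 15 recruited patients each, or 12 after the drop-out allowance (3.4); four steps (section 2); one to four follow-up measurements at five-month intervals (5.3); entry risk of at least 5% (3.2). Assumptions: equal steps, follow-up of 20, 15, 10 and 5 months by step, and a constant hazard. The mean entry risk is not stated, so a range is shown.

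- Recruited: 32 × 15 = 480, or 120 per step. Person-time = 120 × (20 + 15 + 10 + 5)/12 = 500 patient-years.
- Using 12 per cluster throughout: 32 × 12 = 384, or 96 per step. Person-time = 96 × 50/12 = 400 patient-years.
- Annual hazard = −ln(1 − r)/10, where r is the 10-year risk. Expected events = hazard × person-time.

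| 10-year risk r | Annual hazard | Events in 400 patient-years | Events in 500 patient-years |
|---|---|---|---|
| 5% (entry floor) | 0.00513 | 2.1 | 2.6 |
| 10% | 0.01054 | 4.2 | 5.3 |
| 20% | 0.02231 | 8.9 | 11.2 |

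The result depends on follow-up, so a bracket is useful. If all 480 patients were followed for the same time at the 5% floor, expected events = 480 × [1 − 0.95^(months/120)]. This gives 1.0 at 5 months and 4.1 at 20 months, and the chance of at least one event is 64% and 98% respectively.

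These counts include fatal events, which the list catches as deaths. The non-fatal share cannot be derived from the protocol. Other somatic admissions would be additional and are not estimated.

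**The case against.** **AE recording already captures these events.** This is the strongest objection, and it stands as a limit on the point. A reader might infer from the closed list that a non-fatal stroke is never reported, or that the secondary safety parameter would miss it. The protocol does not support that. Section 6.2.1 records it if reported or observed, 6.3 follows it, and 5.1.2 counts AEs by number and type. What is lost is SAE status and everything in 6.2.2 that depends on it.

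**The term may be loose drafting.** The Summary uses the same linking term before a partial list of QRISK3 inputs, while 5.1.1 gives many more, and the rule in 6.2.2 opens with every SAE. A wider meaning is therefore possible. But GPs are given only the four items and no other criterion to apply, so the ambiguity is itself a reason to amend.

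**The section does not strictly contradict itself.** This is correct. Because a suicide attempt can be life-threatening, both reporting classes can be filled from the list. It is a tension between list and classes, and no more.

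**The list matches the risk the protocol identifies.** The Summary and 8.4 name mental destabilisation after a medication change as the risk of participation, and the list reflects that. This explains the choice of items. It does not cover somatic harm from the other actions in Step 3.

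**Sudden cardiac death.** The Introduction says "antipsychotics cause a dose-related increased risk of sudden cardiac death". A reader might cite this as an uncovered event, but death is on the list.

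**Other oversight exists.** Section 6.1 allows suspension on safety grounds and 5.4 allows withdrawal for urgent medical reasons, so SAE reporting is not the only safeguard. Suspension does depend on information reaching the sponsor, and for these events no expedited route is defined.

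**The event counts are not counts of lost reports.** This is also correct. They include fatal events, and the non-fatal ones can still be recorded as AEs.

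**Conclusion.** The point holds in this form: as written, 6.2.2 confines GP notification of SAEs to four events and supplies no general seriousness criterion. Non-fatal infarction, stroke and other life-threatening or hospitalised somatic events are therefore at most passively recorded as AEs. They bypass investigator warning, causality review and expedited reporting, and they would be misclassified in the AE/SAE counts. The claim does not extend to total loss of these events.

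The size is modest in number but relevant to participant safety: roughly 2 to 2.6 cardiovascular events at the entry floor and 9 to 11 at a mean risk of 20%, fatal events included, plus an unknown number of other somatic admissions. This rests on the follow-up pattern, equal steps and constant hazard assumed above. The textual conclusion needs none of these assumptions. Neither primary outcome analysis depends on SAE classification.

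**What to change.** - In 6.2.2, replace the closed list with general seriousness criteria: death, life-threatening event, hospital admission or its prolongation, lasting disability, or another important medical event.
- Keep psychosis, (attempted) suicide, crisis-team involvement and death as events that are always reported as serious.
- Reconcile the definition with the two reporting classes later in the same section, so that the life-threatening class and the remaining class both follow from it.
- Consider naming the non-fatal cardiovascular events, for which the disease list in 3.3 could serve. The exact set of events and any exemptions are for the sponsor and METC to settle.

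The cost is an amendment to the wording, the GP instruction and the SAE form, with somewhat more SAE reports to process.
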